I agree to conduct this study in full accordance with all applicable regulations and Good Clinical Practices (GCP).

Investigator Signature

Name

Date of Signature (DD MMM YYYY)

PROTOCOL SUMMARY

OBJECTIVES

To conduct a prospective observational study assessing a unique outpatient care model in which syncope patients are provided with, and trained to use, a wearable defibrillator prior to discharge from the emergency department (ED). Observational data will be collected to assess the logistics of equipping patients with the device and providing training in the ED, and the ability of patients to receive follow-up care on an outpatient basis. In addition, data will be collected to confirm that the device meets expected safety. The experience gained from this stage of the study will be used to guide future studies of device's functionality enhancements and definitive device safety and efficacy.

STUDY POPULATION

Participants will be patients presenting to the ED following a syncopal event which has been defined as cardiac, or potentially cardiac, i.e. undiagnosed in nature.

INTERVENTION

A wearable defibrillator optimized for short-term ambulatory use with adhesive electrodes will be prescribed for up to 14 days of use following emergency department discharge or until the physician responsible for the subject's care defines an alternative treatment plan.

STUDY DESIGN

This is a single-arm feasibility study.

STUDY SIZE

The study will enroll a minimum of 50 and a maximum of 80 subjects. A maximum of 20 centers will be used for enrollment.

1. INTRODUCTION

Syncope, a transient loss of consciousness that spontaneously resolves without intervention, is one of the leading causes of hospitalization in the United States, making up 1.9% of hospital admissions from the emergency department (ED) and 1.3% of all hospital admissions.^{1,2}

Patients presenting to the ED following a syncopal event receive a clinical work-up to help identify the etiology of the event, which in turn is used to establish the patient's risk of suffering subsequent adverse events. When medical staff are able to identify the underlying cause of syncope, events are diagnosed as being cardiac, neurally mediated, or due to orthostatic hypotension.³ Once etiology is defined and the level of risk has been established, the patient can be triaged appropriately. However, the ED staff is frequently unable to diagnose the nature of the event. This is largely due to the episodic nature of syncope and the inability of patients to provide an accurate recounting of the event.^{4,5} Following history taking and physical examination in the ED, 40% of syncope cases remain undiagnosed.⁶

When the ED staff is able to determine that the syncopal event is related to underlying cardiovascular dysfunction, the patient is considered to be at high risk of suffering a subsequent adverse event, including sudden cardiac death, and is routinely admitted to the hospital.^{7,8} The American College of Emergency Physicians' most recent clinical policy on the management of syncope within the ED states that the primary reason patients should be admitted is to mitigate the risk of significant dysrhythmia or sudden death.⁵ However, in the event that no clear diagnosis is established and cardiac syncope cannot be clearly dismissed, patients are still frequently admitted to mitigate the unknown level of risk. Retrospective chart review has shown that cardiac syncope is believed to account for only 9.5% to 12% of syncope cases.^{9,10} Yet, 30% to 55% of ED presenting syncope patients are still admitted to the hospital.^{2,11} When admitted to the hospital, patients rarely undergo diagnostic cardiac testing beyond basic monitoring, and as much as 42% of patients who are admitted are discharged without a clear cause for the event being established.¹² Further complicating the issue of inappropriate syncope admissions is the fact that roughly one third of ED-presenting syncope patients with indications of cardiovascular disease are still discharged from the ED despite being at high risk of suffering a subsequent adverse event.²

Consistent with this discrepancy between the occurrence of high-risk syncope cases and the syncope hospital admission rate is the body of work in emergency medicine literature aimed to more accurately identify at-risk syncope patients while safely reducing the number of syncope-related hospital admissions. Several syncope risk stratification models have been proposed to improve the rate of appropriate hospital admissions.^{4,11,13-16} These models generally incorporate patient medical history to help risk stratify, which is intended to make them particularly useful when explicit evidence of cardiovascular dysfunction is not obtained during the ED workup. However, despite efforts to develop syncope management tools, it is has been stated that an adequately validated post-ED triage model has not been developed.¹⁷ Current syncope admission practices, in which low risk patients are routinely admitted, place considerable financial burden on the healthcare systems while offering questionable diagnostic and therapeutic yields.¹ Furthermore, admitting low risk patients may unnecessarily expose them to hospital-specific hazards, including hospital-acquired infections, as well as economic loss and emotional disturbance.¹⁸

Advancements in ambulatory cardiac monitoring technology have promoted capturing evidence of transient cardiac events on an outpatient basis, and thus have proven useful in diagnosing the cause of syncope of unknown origins in certain groups of patients.³ Enhanced recording and transmission capabilities and minimally obtrusive form factors help these devices to have minimal effect on quality of life during extended continuous monitoring sessions that may last up to weeks (K113187, K113862). While such devices potentially offer enhanced diagnostic utility and may even detect the onset of life-threatening events, they are incapable of providing time-critical life-saving treatment when adverse events occur. The lack of treatment functionality renders these devices inappropriate for outpatient use when patients are at known risk of suffering life-threatening arrhythmias, and they fail to fully mitigate the uncertain risk faced by patients for whom the cause of syncope has not yet been identified.

It is apparent that the ED staff has come to rely on hospital admission to mitigate the poorly defined risk of sudden cardiac death in syncope patients due to the complexities of diagnosing the underlying cause of syncope in the ED, the lack of adequately validated risk stratification tools, and the inability of currently-available outpatient devices to provide emergency intervention. It would therefore be desirable to utilize a wearable cardioverter defibrillator (WCD) as an integral component of syncope patient management; the WCD would offer patients protection from ventricular arrhythmias while care is managed on an outpatient basis, thus mitigating risk while reducing dependence on hospital admission.

WCDs have been prescribed to offer patients protection from lethal ventricular arrhythmias for both primary and secondary prevention. While worn, WCDs provide outpatient defibrillation faster than can be delivered by emergency medical services because event detection is automatic and the device is already positioned to deliver treatment. Since a WCD is non-invasive and can easily be removed, it makes an ideal device for protecting patients until long-term cardiovascular risk can be adequately defined.

The LifeVest WCD has been commercially approved for use by the FDA and CE marked for Europe since 2001, and over 100,000 patients have worn the device (P010030). Several published articles included in Appendix A demonstrate the impact the LifeVest WCD has had in successfully resuscitating patients from ventricular tachyarrhythmia, with a first shock success rate of 98% for sustained ventricular arrhythmias and a rate of 92% survival to conscious emergency room arrival. This survival rate is far superior to any other form of outpatient resuscitation, which has been reported at 16% in patients who suffer ventricular tachycardia / fibrillation relying on human-mediated resuscitation.¹⁹

The LifeVest WCD is ideal for continuous ambulatory wear that may last up to several months due to use of adhesive-free, dry electrodes. The electrodes are held in place by a reusable garment worn under the patient's clothing. The garment is fit for the patient based on their body-size. Patients are instructed to launder this garment regularly, and thus must be trained to disassemble the garment-electrode belt assembly and reassemble using the second garment which they are supplied.

In addition to the dry electrodes of the LifeVest most commonly used, another model using traditional adhesive electrodes has received approval for shorter term use (P010030/S0005). Using such an electrode configuration would be ideal for equipping patients with a wearable defibrillator prior to ED discharge for shorter term outpatient use. Because adhesive electrodes need to be removed or reapplied less frequently and have no associated garment, the patient's daily interaction with the electrodes is simplified as is their associated training. Furthermore, the requirements placed on the ED staff members who equip the patient with the WCD are simplified since the placement of adhesive defibrillation and electrocardiographic monitoring electrodes translates better to their existing skill set than does garment fitting.

Thus, the wearable defibrillator offers functionality that can significantly improve the management of patients that present to the ED with syncope. However, syncope is not an indication for the currently-approved wearable defibrillator, which is rarely prescribed from the ED. It would be appropriate to conduct a feasibility study to evaluate how a short-term use wearable defibrillator (SWD) may best be incorporated into syncope patient management protocols. Feasibility will be specifically assessed concerning the logistics of equipping patients with the device and providing training in the ED, and the ability of patients to receive follow-up care on an outpatient basis.

2. DEVICE DESCRIPTION

A complete description of the operation and management of the SWD 1000 is given in the Operator Manual.

2.1 Operative Summary

The SWD 1000 uses adhesive ECG monitoring electrodes to continuously collect the patient's electrocardiographic signal. The signal is analyzed for the presence of ventricular tachycardia or ventricular fibrillation (VT/VF) using the same algorithm as the commercially available LifeVest WCD. If VT/VF is detected, the patient undergoes a responsiveness test, which is an alarm sequence that lasts at least 25 seconds. The patient is trained and expected, if conscious, to react to these alarms by holding the response buttons of the SWD 1000, stopping the alarm sequence. If the patient responds but at some point loses consciousness and releases the response buttons, the SWD 1000 will restart the alarm sequence if still in VT/VF. The alarm sequence begins with audible tones that escalate in volume, and later in the sequence voice warnings are given to bystanders alerting them of an impending shock to be given. When the alarm sequence finishes, a defibrillation shock will be delivered to the patient. If at any time during the alarm sequence the response buttons are held or momentarily pressed and released, defibrillation will be delayed. If VT/VF stops before defibrillation, the alarms will be terminated and the defibrillation shock will not be delivered. The SWD 1000 will also detect the presence of bradycardia and asystole using the same algorithm as the commercially available LifeVest. In the event that bradycardia or asystole are detected the monitor will issue an alarm and provide messaging instructing bystanders to contact emergency medical service. As currently designed, the SWD 1000 will not provide electrical therapy in response to bradycardia or asystole.

2.2 Components

The SWD 1000 includes a wiring harness with connections for adhesive ECG and therapy (i.e. defibrillation) electrodes, a monitor/defibrillator ("monitor"), and a holster. The monitor is carried in the holster that can be worn on the patient's hip or supported by an over the shoulder strap. The entire SWD 1000 has a weight of approximately two pounds. The adhesive electrode configuration consists of three ECG electrodes and two therapy electrodes. The system is designed to use FDA-cleared ZOLL adhesive therapy electrodes.

The monitor enables patient interaction via a touch-sensitive LCD display and response buttons recessed on the sides of the unit. The display and speaker are used to communicate messages to the patient and caretakers. In the event of a detected arrhythmia and subsequent alarm sequence, the patient can depress the response buttons to indicate that they are conscious and the shock delivery is subsequently delayed.

The monitor contains the digital signal processing computer, a removable solid-state data storage device, and defibrillation electronic circuitry. The signal processor detects the presence of VT/VF, and asystole/near asystole (severe bradycardia). The defibrillation circuitry, including capacitors and batteries, will deliver up to five truncated exponential biphasic defibrillation pulses, as necessary, to convert a treatable VT/VF episode. The delivered energy of these pulses in this study will be programmed for 150 Joules.

2.3 Support Equipment

The support equipment for the SWD 1000 consists of two rechargeable batteries and a battery charger. Batteries are to be exchanged every 24 hours. Each battery, if fully charged when applied, can deliver five full energy shocks after monitoring the patient for 24 hours. The charger also establishes a wireless connection with the SWD 1000 monitor and transmits data collected by the monitor over a cellular network to a secure server.

2.4 Documents referenced

20B0058: Wearable Defibrillator Model SWD-1000 Clinician Manual
(Referred to as "Clinician Manual")

20B0059: Wearable Defibrillator Model SWD-1000 Patient Manual
(Referred to as "Patient Manual")

3. STUDY OBJECTIVES

The objectives of this feasibility study focus on demonstrating that patients presenting to the ED following a cardiac or potentially cardiac syncopal event, i.e., undiagnosed in nature, may be managed as outpatients and protected from sudden cardiac death by equipping them with, and training them to use, the SWD 1000 prior to ED discharge. Capturing accurate data on patient and caregiver behavior is critically dependent on utilizing the device in a real-world clinical setting.

- 3.1 To observe the level of care provided to SWD 1000-equipped syncope patients on an outpatient basis.
- 3.2 To confirm that the SWD 1000 meets expected safety. Monitoring quality will be used as a surrogate for safety in this feasibility study. Specifically, on average monitoring will be inhibited by noise no greater than 2% of the time worn and monitoring using single lead analysis will be no greater than 5% of the time worn.

It is not anticipated that any treatable events will be observed during this testing period. However, should any events occur, it is expected that the device will yield results at least comparable to those obtained through experience with the currently-approved LifeVest wearable defibrillator.

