6.2 Data Evaluation

6.2.1 Safety Evaluation

The SWD 1000 safety endpoint will be evaluated based on signal quality. ECG quality relates to both safety (poor ECG quality may lead to inappropriate detections and/or shocks) and efficacy (poor ECG quality may interfere with the detection of a ventricular arrhythmia). The criteria for success are that 1) at least one lead is available for ECG monitoring (signal quality acceptable for algorithm input on one or more leads) for $\geq 98\%$ of the time the device is attached to the patient and 2) both leads are available for $\geq 95\%$ of the time the device is attached to the patient. The evaluation will be an average derived from all patients using the internal device flags regarding algorithm performance.

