9. TRIAL DESIGN AND STUDY SIZE

The study is a single arm, open enrollment feasibility study. A maximum of twenty clinical sites will be used to enroll subjects. The multi-site approach is intended to increase variability in the observation of ED characteristics, such as differences in staffing, staff responsibilities, and patient demographic.

A minimum of 50 subjects and a maximum of 80 subjects will be enrolled. The sample size is based on the expected safety objective, which states:

"Specifically, on average monitoring will be inhibited by noise no greater than 2% of the time worn and monitoring using single lead analysis will be no greater than 5% of the time worn."

This objective was taken directly from the LifeVest System Input Requirements (90A0118):

"[R274] Monitoring shall be inhibited by noise no greater than 2% of the time worn on average within the intended patient populations. [R275] Monitoring using single lead analysis shall occur no greater than 5% of the time worn on average within the intended patient populations."

In 2012, the device records of approximately 14,000 patients who used the LifeVest 4000 system were analyzed to determine the system performance. The device records the time when the device is on, when

each of the two ECG channels is determined to be unsuitable for determining the presence of an arrhythmia, and when both leads are determined to be unsuitable. Using these, the time the device was unable to monitor (DUAL) and the time the device was using only a single lead for monitoring (SINGLE) was determined. Each patient's proportion of time spent in SINGLE or DUAL was calculated, then overall descriptive statistics were derived using Excel spreadsheet functions:

	SINGLE	DUAL
Mean	.040	.005
Standard Deviation	.051	.015
Median	.024	.002
Maximum	.762	.644
Minimum	.000	.000
Standard Error	.000431	.000127
95% lower bound	.039989	.004997
95% upper bound	.040011	.005003

The performance of the SWD 1000 is expected to be similar to the 4000 system. A confidence interval of 80% to 90% was used to define expectations of meeting the safety objective for the feasibility stage. A general formula for calculating sample size based on a confidence interval was used:

$$n = \left(2z_{\frac{\alpha}{2}}\sigma/L\right)^2$$

To calculate the sample size for SINGLE performance of the SWD 1000 against the 4000 system:

Confidence: 80%

$$z_{\frac{\alpha}{2}} = 1.28$$

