Allowable difference = 0.01 (0.05 permitted, 0.04 is current 4000 performance)

$$L = 0.02$$

Standard deviation = 0.051 (assumed to be similar to the 4000)

$$n = \left(2z_{\frac{\alpha}{2}}\sigma/L\right)^2 = 42$$

Confidence: 90%

$$z_{\frac{\alpha}{2}} = 1.645$$

Allowable difference = 0.01 (0.05 permitted, 0.04 is current 4000 performance)

$$L = .02$$

Standard deviation = 0.051 (assumed to be similar to the 4000)

$$n = \left(2z_{\frac{\alpha}{2}}\sigma/L\right)^2 = 71$$

To calculate the sample size for DUAL performance of the SWD 1000 against the 4000 system:

Confidence: 90%

$$z_{\frac{\alpha}{2}} = 1.645$$

Allowable difference = 0.01 (0.02 permitted, 0.005 is current 4000 performance)
 $L = 0.02$

Standard deviation = 0.015 (assumed to be similar to the 4000)
 $n = \frac{(2z_{\alpha/2}\sigma)^2}{L^2} = 7$

Thus, a sample size of 50 to 80 subjects is expected to demonstrate that both SINGLE and DUAL performance meet the safety objective of the feasibility study.

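### The both-leads success criterion in 6.2.1 is stricter than the single-lead limit in objective 3.2, on which the trial was sized, and the plan does not say which decides

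*Combined protocol and SAP*

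**What the plan says.** Objective 3.2 uses monitoring quality as the surrogate for safety and sets two limits. Time when noise stops the device from monitoring may average at most 2% of wear time. For the loss of one lead, the limit is that "monitoring using single lead analysis will be no greater than 5% of the time worn". Section 9 repeats this as the basis of the sample size and traces it to the LifeVest input requirements, where R275 reads "Monitoring using single lead analysis shall occur no greater than 5% of the time worn on average within the intended patient populations".

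Section 9 also defines the two quantities taken from the LifeVest 4000 records: "the time the device was unable to monitor (DUAL) and the time the device was using only a single lead for monitoring (SINGLE". The sizing compares a SINGLE mean of 0.040 with a limit of 0.05, and a DUAL mean of 0.005 with a limit of 0.02. It concludes that a "sample size of 50 to 80 subjects is expected to demonstrate that both SINGLE and DUAL performance meet the safety objective".

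Section 6.2.1 states the criteria for success in terms of lead availability. The first asks that "at least one lead is available for ECG monitoring (signal quality acceptable for algorithm input on one or more leads") for at least 98% of attached time. The second asks that "both leads are available for" at least 95% of it. Both are judged on an average over all patients, taken from the device flags.

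**The concern.** Criterion 1 of 6.2.1 is the 2% limit of objective 3.2 turned round: at least one lead for 98% of the time is the same as DUAL of at most 2%. Criterion 2 looks like the same step applied to the 5% limit, but it is not. Time without both leads includes DUAL as well as SINGLE, so criterion 2 limits the sum of the two to 5%.

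This is the study's only quantitative pass/fail test, and Section 10 treats it as a primary objective. If the result falls between the two rules, one part of the protocol calls it a success and another a failure. The choice between them could then be made with the data in hand. The sizing statement in Section 9 was also never checked against the rule that 6.2.1 labels as the criterion for success.

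**Working it through.** **Inputs.** From Section 9: SINGLE mean 0.040, SD 0.051; DUAL mean 0.005, SD 0.015; z = 1.28 (80%) and 1.645 (90%); n = (2zσ/L)²; 50 to 80 subjects. From 3.2: SINGLE ≤ 0.05, DUAL ≤ 0.02. From 6.2.1: at least one lead ≥ 0.98, both leads ≥ 0.95.

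**1. The plan's own figures.**
- SINGLE, 80%: (2 × 1.28 × 0.051 / 0.02)² = 42.6 (plan: 42, apparently truncated).
- SINGLE, 90%: (2 × 1.645 × 0.051 / 0.02)² = 70.4, rounded up to 71 (plan: 71).
- DUAL, 90%: (2 × 1.645 × 0.015 / 0.02)² = 6.1, rounded up to 7 (plan: 7).

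The sizing therefore reproduces, for SINGLE and DUAL taken separately.

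**2. The two rules on one scale.** With two channels and exclusive states, both-leads time = 1 − SINGLE − DUAL. Criterion 2 is therefore SINGLE + DUAL ≤ 0.05.

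| SINGLE | DUAL | Both leads | 3.2 | 6.2.1 |
|---|---|---|---|---|
| 4.0% | 0.5% | 95.5% | met | met |
| 4.8% | 0.5% | 94.7% | met | failed |
| 4.5% | 1.0% | 94.5% | met | failed |
| 5.0% | 2.0% | 93.0% | met (at both limits) | failed |

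The conflict runs one way. If SINGLE + DUAL ≤ 5%, then SINGLE ≤ 5%, so with a common denominator a pass of 6.2.1 is also a pass of 3.2.

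**3. Margin.** At the LifeVest means the sum is 0.040 + 0.005 = 0.045. The distance to 0.05 is 0.005, so L = 0.01, half the 0.02 used for sizing.

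**4. SD of the sum.** The plan does not give it. It depends on the between-patient correlation of SINGLE and DUAL, which has to be assumed:
- correlation −1: 0.051 − 0.015 = 0.036
- uncorrelated: √(0.051² + 0.015²) = 0.0532
- correlation +1: 0.051 + 0.015 = 0.066

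**5. Results under the both-leads rule.** Sample size is (2z × SD / 0.01)². The chance that the observed mean meets the limit is Φ(margin × √n / SD), by normal approximation, if the true means equal the LifeVest means. For example, uncorrelated at n = 50: 0.005 × √50 / 0.0532 = 0.665, giving 0.747.

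| Rule | SD | n, 80% | n, 90% | P(pass), n = 50 | P(pass), n = 80 |
|---|---|---|---|---|---|
| SINGLE alone | 0.051 | 42 (plan) | 71 (plan) | 0.917 | 0.960 |
| Sum, correlation −1 | 0.036 | 85 | 141 | 0.837 | 0.893 |
| Sum, uncorrelated | 0.0532 | 186 | 306 | 0.747 | 0.800 |
| Sum, correlation +1 | 0.066 | 286 | 472 | 0.704 | 0.751 |

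On the plan's own two-sided confidence scale (2P − 1), the both-leads rule gives 41–67% at n = 50 and 50–79% at n = 80, against 83% and 92% for SINGLE alone.

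**6. How often the verdicts differ.** SINGLE and DUAL were simulated as lognormal, matched to the Section 9 means and SDs, with 20,000 trials per setting. The share of trials that meet 3.2 and fail 6.2.1 was:

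| Log-scale correlation | n = 50 | n = 80 |
|---|---|---|
| −0.5 | 12.3% | 12.4% |
| 0 | 13.6% | 13.5% |
| 0.5 | 14.7% | 14.8% |
| 0.9 | 15.9% | 16.1% |

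The reverse never occurred, as step 2 requires.

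**The case against.** The strongest reply is that 6.2.1 is the only place that states criteria for success, and it names the summary measure and data source, so it is the operative rule; 3.2 only states an aim. On that reading the decision rule is prespecified and only the sizing is off. The reading is fair but not secure, because Section 9 sizes the trial on the 3.2 wording and calls it the safety objective. If 6.2.1 does govern, the sizing claim is unsupported; if it does not, 6.2.1 misstates the test.

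It can also be said that this is a single-arm feasibility study with a surrogate endpoint, that definitive safety is left to later studies, and that the stricter rule errs on the cautious side. All true, and it limits the harm: a device that passes 6.2.1 cannot falsely pass 3.2, and no data are lost. It does not remove two conflicting verdicts on a primary objective.

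Three technical points stand as qualifications:
- Section 6.2.1 compares an observed mean with a limit, so the pass probability describes the shortfall better than 2P − 1, which also counts unusually low noise as a miss.
- Correlations of −1 and +1 are outer bounds. Lognormals matched to the table can reach only about −0.20 to +0.90, which gives about 165–275 subjects (80%) and 272–455 (90%), still far above 80.
- The one-way result assumes that time worn (3.2) and time attached (6.2.1) are the same denominator. The protocol does not say so, and Section 5.5 lets subjects shower with electrodes on and the monitor off.

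At the LifeVest means both rules are met, and the simulated verdicts agree in about 84–88% of trials.

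**Conclusion.** The inconsistency is real and follows from the protocol's own definitions. It would disappear only if SINGLE included DUAL, which the Section 9 definition rules out. Neither Section 10 nor Section 13 reconciles the two rules.

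For a device that performs exactly like the LifeVest 4000, the both-leads rule halves the margin and lowers the pass probability at 50 subjects from 92% to 70–84%, and at 80 subjects from 96% to 75–89%. It leaves about 12–16% of trials with opposite verdicts. No correlation brings the sample size by the plan's formula within 80.

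The contradiction itself needs no assumption beyond exclusive states. The sizes assume the LifeVest means and SDs, a normal approximation or lognormal shape, the stated correlation range and a common denominator. The gap is one of prespecification and should be closed before data are seen.

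**What to change.** Before data are seen, adopt one rule and use it in 3.2, 6.2.1 and Section 9.

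- **Option A.** Restate criterion 2 of 6.2.1 as mean SINGLE time of no more than 5% of time worn. This matches 3.2, R275 and the existing sizing. It costs wording only, but it relaxes the success criterion now written in 6.2.1, and the protocol should say so openly.
- **Option B.** Keep the both-leads criterion and change 3.2 to SINGLE + DUAL of no more than 5%. Restate Section 9 with the 0.005 margin, the SD of the sum computed from the approximately 14,000 LifeVest records already analysed, and the resulting confidence at 50 to 80 subjects. It costs wording and one SD from existing data. The price is accepting, and stating, a lower confidence than the plan now claims.

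Under either option, use one denominator throughout and define it, and report mean SINGLE, mean DUAL and mean both-leads time with confidence intervals. All three come from the device flags, so neither option needs extra patients or new data collection.
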